6.7 Other assessments

6.7.2 Pharmacokinetics

Blood collection and processing

All blood samples will be taken anytime during the visit except at Visit 3 (Randomization), Visit 5 (Month 1) and Visit 17 (Month 1 of Extension Phase).

At Visit 3, one blood sample will be collected before administration of the study drug (oral capsule), and another one approximately 6 hours post-dose (oral capsule).

At Visit 5 and Visit 17, one blood sample will be collected at pre-dose (24 hours post last dose of the study drug, and before the new administration) and a second collection approximately 6 hours post-dose. Patients should be instructed NOT to take the dose at home on this day of the visit. Instead they should be asked to bring the fingolimod capsule with them to the visit and take it after the pre-dose sample is drawn.

Blood samples (1.8 mL) will be collected into a sodium citrate vacuum tube, by either direct venipuncture or an insertion of an indwelling cannula into a forearm vein. Immediately after each tube of blood is drawn, it should be inverted gently several times to ensure the mixing of tube contents (e.g., anticoagulant). Prolonged sample contact with the rubber stopper should be avoided. The tube should be placed upright in a test tube rack surrounded by ice until transfer. Within 30 min of blood collection the tubes must be frozen at $\leq -18^{\circ}\text{C}$ and must be transferred to a $\leq -70^{\circ}\text{C}$ freezer within 3 months of collection pending analysis. Alternatively, the tubes can be transferred directly to a $\leq -70^{\circ}\text{C}$ immediately after sample collection.

All samples will be given a unique sample number. The actual dosing date and time and actual sample collection date and time will be entered on the PK blood collection page of the eCRF. Sampling problems will be noted in the Notes field of the eCRFs.

Blood samples will be shipped to the central laboratory on a regular basis, except those from Visit 5 and Visit 17 that should be sent as soon as possible after collection to allow for the online pharmacokinetic analysis (i.e. those samples drawn from patients with a body weight of 40 kg or less).

Details on labeling of the pharmacokinetic samples and shipment instructions will be included in the laboratory manual provided by the Central Laboratory.

Analytical Method

Fingolimod and fingolimod-P will be measured in whole blood using a validated LC-MS/MS with a LLOQ of 0.020 ng/mL and of 0.025 ng/mL, respectively.

7 Safety monitoring

7.1 Adverse events

An adverse event is the appearance or worsening of any undesirable sign, symptom, or medical condition occurring after starting the study drug even if the event is not considered to be related to study drug. Study drug includes the investigational drug under evaluation and the comparator drug or placebo that is given during any phase of the study. Medical conditions/diseases present before starting study drug are only considered adverse events if they worsen after starting study drug. Abnormal laboratory values or test results constitute adverse events only if they induce clinical signs or symptoms, are considered clinically significant, or require therapy.

The occurrence of adverse events should be sought by non-directive questioning of the patient at each visit during the study. Adverse events also may be detected when they are volunteered by the patient during or between visits or through physical examination, laboratory test, or other assessments. All adverse events must be recorded on the Adverse Events eCRF with the following information:

1. the severity grade (mild, moderate or severe)
2. its relationship to the study drug(s) (suspected/not suspected)
3. its duration (start and end dates or if continuing at final exam)
4. whether it constitutes a serious adverse event (SAE)

An SAE is defined as an event which:

- is fatal or life-threatening
- results in persistent or significant disability/incapacity
- constitutes a congenital anomaly/birth defect
- requires inpatient hospitalization or prolongation of existing hospitalization, unless hospitalization is for:
 - routine treatment or monitoring of the studied indication, not associated with any deterioration in condition (e.g. hospitalization for relapse treatment)
 - routine treatment or monitoring of the studied indication, not associated with any deterioration in condition
 - elective or pre-planned treatment for a pre-existing condition that is unrelated to the indication under study and has not worsened since the start of study drug
 - treatment on an emergency outpatient basis for an event not fulfilling any of the definitions of a SAE given above and not resulting in hospital admission
 - social reasons and respite care in the absence of any deterioration in the patient's general condition
- is medically significant, i.e. defined as an event that jeopardizes the patient or may require medical or surgical intervention to prevent one of the outcomes listed above

Unlike routine safety assessments, SAEs are monitored continuously and have special reporting requirements; see [Section 7.2](#).

All adverse events should be treated appropriately. Treatment may include one or more of the following: no action taken (i.e. further observation only); study drug dosage adjusted/temporarily interrupted; study drug permanently discontinued due to this adverse event; concomitant medication given; non-drug therapy given; patient hospitalized/patient's hospitalization prolonged. The action taken to treat the adverse event should be recorded on the Adverse Event eCRF.

Once an adverse event is detected, it should be followed until its resolution or until it is judged to be permanent, and assessment should be made at each visit (or more frequently, if necessary) of any changes in severity, the suspected relationship to the study drug, the interventions required to treat it, and the outcome.

Information about common side effects already known about the investigational drug can be found in the Investigator Brochure (IB) or will be communicated between IB updates in the form of Investigator Notifications. This information will be included in the patient informed consent and should be discussed with the patient during the study as needed.

7.2 Serious adverse event reporting

To ensure patient safety, every SAE, regardless of suspected causality, occurring after the patient has provided informed consent and until 3 months after the patient has stopped study participation (defined as time of last dose of study drug taken or last visit whichever is later) must be reported to Novartis within 24 hours of learning of its occurrence.

Any SAEs experienced after this 3 months period should only be reported to Novartis if the investigator suspects a causal relationship to the study drug.

Recurrent episodes, complications, or progression of the initial SAE must be reported as follow-up to the original episode, regardless of when the event occurs. This report must be submitted within 24 hours of the investigator receiving the follow-up information. An SAE that is considered completely unrelated to a previously reported one should be reported separately as a new event.

Information about all SAEs is collected and recorded on the Serious Adverse Event Report Form. The investigator must assess the relationship of any SAE to study drug, complete the SAE Report Form in English, and send the completed, signed form by fax within 24 hours to the local Novartis Drug Safety and Epidemiology Department. The telephone and telecopy number of the contact persons in the local department of Drug Safety and Epidemiology, specific to the site, are listed in the investigator folder provided to each site. The original copy of the SAE Report Form and the fax confirmation sheet must be kept with the case report form documentation at the study site.

Follow-up information is sent to the same person to whom the original SAE Report Form was sent, using a new SAE Report Form stating that this is a follow-up to the previously reported SAE and giving the date of the original report. The follow-up information should describe whether the event has resolved or continues, if and how it was treated, whether the blind was broken or not, and whether the patient continued or withdrew from study participation.

If the SAE is not previously documented in the Investigator's Brochure or Package Insert (new occurrence) and is thought to be related to the Novartis study drug, a Drug Safety and

Epidemiology Department associate may urgently require further information from the investigator for Health Authority reporting. Novartis may need to issue an Investigator Notification (IN) to inform all investigators involved in any study with the same drug that this SAE has been reported. Suspected Unexpected Serious Adverse Reactions (SUSARs) will be collected and reported to the competent authorities and relevant ethics committees in accordance with Directive 2001/20/EC or as per national regulatory requirements in participating countries.

Although MS relapses are considered medically significant and are frequently associated with hospitalization and thus, meet the definition for SAEs, these events will be reported on the MS relapse eCRF instead of the SAE form unless, in the judgement of the investigator, a MS relapse is unusually severe or unexpected and warrants specific notification as an SAE.

7.3 Pregnancies

To ensure patient safety, each pregnancy in a patient on study drug must be reported to Novartis within 24 hours of learning of its occurrence and the study drug needs to be discontinued immediately. The pregnancy should be followed up to determine outcome, including spontaneous or voluntary termination, details of the birth, and the presence or absence of any birth defects, congenital abnormalities, or maternal and/or newborn complications.

Pregnancy should be recorded on a Clinical Trial Pregnancy Form and reported by the investigator to the local Novartis Drug Safety and Epidemiology Department. Pregnancy follow-up should be recorded on the same form and should include an assessment of the possible relationship to the study drug of any pregnancy outcome. Any SAE experienced during pregnancy must be reported on the SAE Report Form.

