6.6 Pregnancy and assessments of fertility

Females of child-bearing potential are defined as all females physiologically capable of becoming pregnant. This includes female children and adolescents who are menarchal or who become menarchal during the study.

Serum pregnancy test will be performed by the central laboratory for all females of child-bearing potential according to the schedule in [Table 6-1](#) and [Table 6-3](#).

Although it is expected that this study will enroll mostly girls who are not sexually active, some may be sexually active. All menarchal girls and their parents/caregivers should be informed about the potential risks of pregnancy and the need to prevent pregnancy during the study.

It is important to be sensitive in introducing this issue, as understanding and comprehension of a child about puberty, sexual activity, pregnancy and contraception varies with age. These discussions with the patient and her parents/caregivers are therefore best performed by investigators familiar with the child/adolescent and her family and are part of the circle of care. The investigator should also discuss the management of the pregnancy test results with the patient and her parents/caregivers. These discussions may vary across countries and regions and should be guided by requirements of the local regulatory authority.

Female patients of childbearing potential who are sexually active will perform a urine pregnancy test (e.g. via home pregnancy test kit) monthly (in the months between clinic Visits and serum pregnancy testing). In the event of a positive urine pregnancy test, the patient must immediately contact the investigator. Additional pregnancy tests may be performed at the investigator's discretion during the study. Patients becoming pregnant must discontinue study drug.

[figure not shown]
Female patients of child-bearing potential must be informed of the potential teratogenic risk with fingolimod and the need for highly effective contraception to prevent pregnancy while on study drug and for 2 months after stopping study drug should they be or become sexually active.

Use of a combination of any two of the following methods of contraception (a+b or a+c or b+c) should be used as appropriate:

- a) use of oral, injected or implanted hormonal methods of contraception
- b) placement of an intrauterine device or intrauterine system

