- c) barrier methods of contraception: condom or occlusive cap (diaphragm or cervical/vault caps) with spermicidal foam/gel/film/cream/vaginal suppository

Contraception must be used during the study and for 2 months after stopping study drug. The decision on the contraceptive method should be reviewed at least every 3 months to evaluate the individual need and compatibility of the method chosen.

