3.8.5 Safety data cutoff and visit windows for summaries on follow-up set

For safety summaries on the safety set, only core phase data (defined in 3.8.3) which are within 45 days (5 times the half-life of FTY720, 9 days) after the last dose of study drug. For safety summaries on the follow-up set, all core phase data, including assessments or events more than 45 days after the last dose of study drug in core phase, will be considered.

The time-windows below will be used in summaries on the follow-up set.

- 1) Day 1 to 45 after drug discontinuation
- 2) >Day 45 after drug discontinuation

For each of the time-window, assessments collected or events started during the specified day intervals after the last dose date will be used. The last dose date defined in Section 3.8.7 will be used to determine day windows.

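### Protocol Section 7.3 does not clearly require reporting or outcome follow-up of a pregnancy conceived after the last dose, although Section 6.6 requires contraception for 2 months after stopping

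*Protocol*

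**What the plan says.** Protocol Section 7.3 sets the trigger: "each pregnancy in a patient on study drug must be reported to Novartis within 24 hours of learning of its occurrence". The same sentence requires study drug to be stopped. The next continues: "The pregnancy should be followed up to determine outcome, including spontaneous or voluntary termination, details of the birth", and goes on to birth defects and to maternal and newborn complications. A second paragraph names the pregnancy form and the recipient, without limiting this to patients on drug, and sends any serious adverse event (SAE) during pregnancy to the SAE form.

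Protocol Section 6.6 gives the reason for concern: "Female patients of child-bearing potential must be informed of the potential teratogenic risk with fingolimod". It also sets a period that outlasts dosing: "Contraception must be used during the study and for 2 months after stopping study drug".

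Protocol Section 7.2 requires SAEs to be reported "until 3 months after the patient has stopped study participation", counted from the later of the last dose and the last visit. After that: "Any SAEs experienced after this 3 months period should only be reported to Novartis if the investigator suspects a causal relationship to the study drug".

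SAP Section 3.8.5 limits safety-set summaries to Core Phase data "within 45 days (5 times the half-life of FTY720, 9 days) after the last dose of study drug".

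**The concern.** The protocol treats the weeks after the last dose as a period in which pregnancy is to be avoided because of possible harm to the fetus. Its mandatory pregnancy report attaches only to patients still taking drug. A girl who stops treatment and conceives a few weeks later is inside the first period and outside the second.

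The on-drug wording cannot be dismissed as loose drafting. Elsewhere the protocol separates patients on and off study drug deliberately, for example when it counts relapses for the primary analysis (Section 9.4.3). Section 7.2 shows that the authors write a post-treatment window when they intend one.

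What is at stake is the completeness of a small but important body of safety data. If off-drug pregnancies enter the safety database only when something goes wrong, or only when an investigator suspects the drug, the normal outcomes and the number of exposed pregnancies are lost. The outcomes that remain are then a selected set. The trial expects some sexually active adolescents, includes a 5-year extension on fingolimod, and is meant to support paediatric approval.

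**Working it through.** There is no statistical figure to reproduce. The check sets the stated windows after the last dose side by side.

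- **Pregnancy report and outcome follow-up** (Protocol 7.3): no period stated.
- **Contraception** (Protocol 6.6): 2 months, about 60 days.
- **Safety-set cutoff** (SAP 3.8.5): 5 × 9 days = 45 days, as the SAP states.
- **SAE reporting** (Protocol 7.2): 3 months after the later of last dose and last visit. Pregnancy is not itself an SAE under Section 7.1; a congenital anomaly is.
- **Extension follow-up visit** (Table 6-3, note 2): 3 months ± 10 days after the last dose. The serum pregnancy row has ten marks across eleven columns. The blank appears to be Visit 15, so the follow-up visit appears to be marked.

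**Size of the gap.** About 60 − 0 = 60 days per patient who stops, of which the first 45 are also inside the SAP's own cutoff.

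**Residual drug.** This uses the SAP's 9-day half-life and assumes simple first-order decay. The fraction left after *t* days is 0.5^(t/9). At 45 days this is 0.5^5 = 3.1%; at 60 days it is 0.5^6.67 = 1.0%. Conceptions early in the 2 months are therefore clearly exposed. This holds for fingolimod only, not for Core Phase patients on interferon.

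**Whether the other rules fill the gap.**

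1. *Second paragraph of Section 7.3.* It has no on-drug limit, but it says which form to use and where to send it. It can be read as covering every pregnancy, or as giving the route for those already caught by the first paragraph. It does not settle the question.
2. *Serum test at the Extension follow-up visit.* It falls about one month after the 2-month period ends, so it could detect a conception within it. A positive result there comes from a patient no longer on drug. Section 7.3 does not say that it must be reported, even if conception preceded the last dose.
3. *SAE during pregnancy.* This captures complications. An uncomplicated pregnancy produces no report and no outcome record.
4. *Congenital anomaly as an SAE.* For a patient who leaves at her last dose, the unconditional window closes 3 months later. If the 3-month follow-up visit counts as her last visit, it closes at about 3 + 3 = 6 months. A term birth from a conception after the last dose falls later than either, so an anomaly is then reportable only if causality is suspected. For a patient who stops drug but stays in the study (Table 6-2 in the Core Phase, or yearly visits in the Extension Phase), the window can run past the birth.

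**The case against.** The strongest reply is that Section 7.3, read as a whole, is at most ambiguous. Only its opening sentence carries the on-drug limit, and that sentence also orders drug to be stopped, which makes sense only for patients taking it. The second paragraph speaks of pregnancy without restriction. Off-drug detection appears to be planned in the Extension Phase. Serum tests go to the central laboratory (Section 6.6) and central results go to the sponsor (Section 8.3), so a positive follow-up test would be visible to both site and sponsor.

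Much of this stands. A reader might infer that pregnancies conceived after the last dose are neither reported nor followed. The documents do not support that: nothing forbids a report, and the second paragraph may prompt one. A reader might also infer that the SAE rule never reaches a birth defect in these cases. That is too strong as well. An anomaly is an SAE, the window runs from the later of last dose and last visit, and suspected cases stay reportable without limit of time.

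What does not stand is the claim that these provisions close the gap. Seeing a positive test is not the same as a duty to report it within 24 hours and follow it to outcome. No provision expressly imposes that duty for an uncomplicated pregnancy conceived off drug.

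**Conclusion.** The mismatch between Sections 6.6 and 7.3 is real. For about 2 months after the last dose, the protocol requires contraception because of potential teratogenic risk, yet it does not clearly require a pregnancy conceived then to be reported or followed to outcome. The late-anomaly problem is narrower: it applies mainly to patients whose participation ends near their last dose.

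Few cases are expected. The protocol itself anticipates mostly girls who are not sexually active, and the documents give no basis for an expected count. The 15% drop-out assumed in Section 9.6 should not be used to size the issue. It was set to project entry to the Extension Phase, and it covers both sexes, both arms and study drop-out rather than stopping drug. No objective, endpoint or efficacy analysis is affected. The point is worth correcting because each missed outcome is consequential and the correction is nearly free.

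The conclusion rests on reading the second paragraph of Section 7.3 as form and route only, and on the Table 6-3 row running through to the follow-up column. Table 6-1 was not in the text available for this review, so Core Phase follow-up testing is unchecked. The pregnancy form instructions were not available either and might settle the scope.

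**What to change.** Reconcile Section 7.3 with Section 6.6. Extend the 24-hour report and the outcome follow-up to any pregnancy with estimated conception within the post-treatment period already stated in Section 6.6, as well as any in a patient on study drug. Make clear that a pregnancy conceived on drug but discovered after the last dose is included. Leave the instruction to stop study drug attached to patients still taking it. State that a positive test at a follow-up visit is handled under the same rule. The length of the post-treatment period is for the sponsor to settle; the point is that the two sections should use the same one.

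The cost is one clause in Section 7.3 and a matching line in the pregnancy form instructions. It adds no test, visit or contraception requirement, and at most a handful of extra reports.

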7.4 Data Monitoring Committee

A Data Monitoring Committee (DMC) will be in place to oversee the study. The DMC will be an external board comprised of various specialists (also relevant to the pediatric MS population being studied). Details will be provided in the DMC charter.

The DMC will be responsible for on-going review of enrollment, safety and, if requested by the DMC, efficacy data and will provide regular assessments on the safety and overall risk to benefit ratio of the study conduct, advise the sponsor of a need for protocol modification/amendment in order to minimize potential risk for patients, request additional information or make recommendation including stopping of enrollment and/or treatment, if needed.

A Novartis designee will be responsible for the timely coordination and delivery of the data to the DMC on a regular basis. The chair of the DMC will be responsible for providing summaries/executive reports of each DMC meeting to Novartis, arranging on-going communication between members of the DMC, arranging meetings and maintaining files with all correspondence pertaining to the study.

The responsibilities of the DMC may be terminated by Novartis once safety review by the DMC is no longer needed.

8 Data review and database management

